the blood contacting surfaces of device inflow cannula or outflow conduit or grafts. This will be reported via direct visual inspection (documented by a photograph if available) on pump removal or by sending the pump back to manufacturer for evaluation. Any pump explanted for suspected device thrombosis will be sent back to manufacturer for analysis. All pump thrombosis events will be adjudicated by an independent committee, the Research Review Committee which is described below in the Data and Safety Monitoring Section.

- For patients who will **die in the hospital within 30 days**, the cause of death will be confirmed by postmortem examination performed by a pathologist who will be unaware of the study assignments.

Secondary Outcome Measures

1. Need for blood product transfusion within 48-hours post LVAD implantation
2. Operative safety outcomes: incidence of 30-day mortality (from the day of surgery to 30 days [+/- 3 days]), chest tube output in the first post-operative 24 hours, rate of post-operative re-exploration for bleeding
3. Incidence of allosensitization at 30-days, 6-months and 12-months post-LVAD implantation. Allosensitization is defined as calculated panel reactive antibody (cPRA) > 10%.
4. Readmission for heart failure (follow-up 1 year)
5. OHP, overall coagulation potential and overall fibrinolytic potential in the perioperative period
6. Major bleeding defined as an episode of suspected internal or external bleeding that results in one or more of the following: death, re-operation, hospitalization, transfusion of red blood cells according to INTERMACS definition.

Other Outcome Measures

1. Duration of surgery (skin incision to skin closure)
2. Duration of postoperative mechanical ventilation (length of time from intubation until patient is extubated)
3. Length of ICU stay (length of time from ICU admission from surgery until ICU discharge)
4. Length of hospital stay (length of time from surgery to hospital discharge)
5. Incidence of renal dysfunction defined by INTERMACS criteria
6. Incidence of 30-day mortality (from the day of surgery to 30 days [+/- 3 days])
7. Incidence of post-operative mortality within 6 months and 1 year

8. Device-related complications totaled at 30-days, 6-months and 12-months post-LVAD implantation.
9. Duration and amount of intraoperative and postoperative inhaled nitric oxide use

COLLECTION OF BASIC DATA/PATIENT CHARACTERISTICS

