After standard cardiac anesthesia, surgical access to the heart for LVAD implantation will be gained through a median sternotomy in all of the patients. Scavenged blood from the operative field will be collected in a cell saver and transfused back to the patient after washing for recovery of red blood cells in all patients. Intra-operative trans-thoracic ultrasound (TEE) will be used on all patients to evaluate for associated pathologies that will require surgical management at the time of LVAD implantation and thereby contraindicate an off-pump approach. All of these procedures (median sternotomy, cell saver and TEE) are standard procedures used in cardiac surgery.

The decision to implant an LVAD on-CPB or off-pump will be made intraoperatively at this point by the surgeon. The surgeon's decision is based upon their test of the hemodynamic stability of the patient by positioning maneuver of the heart. Only patients who will be hemodynamically stable during the positioning of the heart will be included in the study and will be randomized. If the surgeon declares the patient is eligible for an off-pump procedure, a prepackaged envelope will be opened that indicates whether the procedure is to proceed off-pump or if an on-pump procedure will be used. (A pre-specified envelope will be created prior to each surgery with the assistance of REDCap).

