To evaluate the role of CPB on hemostatic and fibrinolytic parameters, we will make sure that the perioperative level of heparinization will be comparable between groups.

All patients will be postoperatively treated with 81mg aspirin daily and coumadin with a target international normalized ratio range of 2.0–2.5. Data on the use of antithrombotic therapy will be recorded at baseline and at each follow-up appointment. Time-in-Therapeutic Range (TTR) will be calculated using the Rosendaal method as a measure of quality of anticoagulation dose management (42).

Use of tranexamic acid

Tranexamic acid is a well-documented fibrinolytic inhibitor. The medical team will be advised to use always the same dose of tranexamic acid (if the patient's condition will allow it) in the perioperative period as it has an effect on overall fibrinolytic potential.

SELECTION OF SURGEONS

All surgical procedures will be performed by an "experienced" cardiac surgeon with more than 5 years of practice in cardiac surgery after residency training and has performed more than 100 LVAD implantations. Primary surgeons have experience with both techniques (on-pump and off-pump LVAD implantation). All procedures will be done under the supervision of an "expert" cardiac surgeon ([name]/PI of this protocol) who has more than 30 years of experience in advanced and complex cases of cardiac surgery, has performed more than 500 LVAD implantations, and is very experienced with both techniques (on-pump and off-pump LVAD implantation). Residents and fellows will not be eligible to participate as primary surgeons in the trial.

BLOOD COLLECTION AND PREPARATION

For research purposes, two additional vials of blood will be collected at the same time that standard of care blood draws are done. The timepoints for the research blood draws will be at baseline (within 48 hours of surgery), within 24-48 hours post-operation (but before discharge), 30 days, 6 months and 1 year. For the follow-up blood draws (+/- 5 days is acceptable).

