As this study used two approved methods, it is a comparative effectiveness model. The risk to the patient is no more than that of any patient undergoing LVAD implantation. As the decision for eligibility for an off-pump is made based upon data and clinical evaluation, the risk of having to convert the procedure to on-pump is very small (less than 6 % of cases). The conversion is done to eliminate the risk of patients that are not able to tolerate the off-pump surgery. In our experience the off-pump insertion of the LVAD has been safe. Patients choosing to enroll in this trial are not at any additional risk as compared to that of having the procedure done outside of this trial. The benefit of participating in this trial is the contribution of novel data that is collected in a randomized fashion and will enable future cases to be decided upon quality evidence bases.

STUDY DATA COLLECTION AND STORAGE

Study data will be collected and managed using the REDCap electronic data capture tool (36). REDCap is a secure, web-based application designed to support data capture for research studies, providing: 1) an intuitive interface for validated data entry; 2) audit trails for tracking data manipulation and export procedures; 3) automated export procedures for seamless data downloads to common statistical packages; and 4) procedures for importing data from external sources.

All data will be stored on the password-protected computers. Only the principal investigator and co-investigators will have access to source documents, which will be password protected. All analysis will be completed on de-identified datasets.

DATA AND SAFETY MONITORING

The research team will follow the international, national, and institutional regulations and standards:

- Any patient that chooses to leave the study will be removed and their data up until that point will be retained in an de-identified fashion.
- Safety monitoring is accomplished through periodic review by the Primary Investigator, who will consult with the a Research Review team which will consist of a cardiac surgeon, a cardiovascular disease specialist, a biostatistician, and a pathologist. None of the Committee members will be directly involved in the study and will not work at our department.
- Further, this protocol will undergo continuing review by the Institutional Review Board at UTHealth.

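### Accumulating safety data are reviewed by the PI, who supervises every operation; the independent committee is consulted but has no stated schedule, by-arm data, access or authority to recommend a pause

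*Combined protocol and SAP*

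**What the plan says.** - **Who monitors safety (Data and Safety Monitoring).** "Safety monitoring is accomplished through periodic review by the Primary Investigator, who will consult with the a Research Review team". The team consists of a cardiac surgeon, a cardiovascular specialist, a biostatistician and a pathologist. Of its independence the section says: "None of the Committee members will be directly involved in the study and will not work at our department".
- **The PI's role in the operations (Selection of Surgeons).** "All procedures will be done under the supervision of an 'expert' cardiac surgeon ([name]/PI of this protocol").
- **The committee's other role (Primary Outcome Measures).** "All pump thrombosis events will be adjudicated by an independent committee, the Research Review Committee".
- **Access.** Study Data Collection and Storage says: "Only the principal investigator and co-investigators will have access to source documents". Data and Safety Monitoring limits data access to the investigators and the coordinators. The committee is on neither list.
- **Other oversight.** Data and Safety Monitoring adds continuing review by the IRB. Primary Outcome Measures has a pathologist who is unaware of assignment confirm the cause of in-hospital deaths within 30 days.
- **The stated conversion risk (Risk and Benefits).** "the risk of having to convert the procedure to on-pump is very small (less than 6 % of cases"). The Surgical Technique section has conversions recorded with their reason and timing, for understanding the techniques and for secondary analysis.

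The protocol gives no review interval, does not say whether reviews are pooled or by arm, sets no criterion for referring a signal, and does not say what the committee may recommend.

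**The concern.** The person who judges whether one technique is doing harm is also responsible for how both are carried out. The protocol records this team's favourable view of off-pump implantation before the trial (Off-pump LVAD surgery; Risk and Benefits) and expects it to do better (Expected Results). This is a structural conflict and implies no misconduct. A run of poor outcomes in one arm can reasonably be put down to individual patients, and the protocol does not require anyone independent to look at the two arms side by side.

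The stakes are mainly patient safety. The composite includes death and renal replacement, and the Background says that no prospective randomised data exist on the risks and benefits of bypass in these patients. There is also a smaller concern about trial conduct. Decisions taken after randomisation, such as conversion, are made by a team whose supervisor reviews the accumulating harms. If those reviews show emerging differences, such decisions could come to differ between the arms.

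**Working it through.** The point rests on who holds which role, so the main check sets the sections side by side.

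| Question | What the protocol gives | What it leaves open |
|---|---|---|
| Who reviews accumulating safety? | The PI, periodically | The interval |
| Is the reviewer independent of the operations? | No: the PI supervises all of them | – |
| Is an independent body available? | Yes: four disciplines, outside the study and the department | – |
| What does that body do? | Is consulted on safety; adjudicates pump thrombosis | When, on what data, with what authority |
| Can it see the data? | On neither access list | Whether anyone must send data to it |
| Who else oversees the trial? | IRB continuing review | Whether the IRB sees comparative data |

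**Does the PI see results by arm?** The protocol does not say so. It is an inference from three stated facts: the PI conducts the periodic review, has source access and supervises every operation. Blinding is stated for outcome assessors, and nothing is stated for the safety review.

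**Could this knowledge bias the comparison?** The order of events matters.

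1. In Surgical Technique the positioning test comes first: "The surgeon's decision is based upon their test of the hemodynamic stability of the patient by positioning maneuver of the heart".
2. Only stable patients are then randomised, by opening an envelope.
3. A drift in the stability threshold therefore changes who enters both arms alike. It affects the population enrolled and, with allocation concealed, does not favour an arm.
4. Conversion comes after allocation and could differ by arm.

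**Scale, using conversions.** Expected conversions = number of off-pump patients × conversion rate. The inputs are 70 per arm (Statistical Methods) and the stated ceiling of 6%. The 20% rate is an assumption for illustration. Off-pump numbers at each review assume an even split.

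| Patients reaching day 30 | Off-pump | At 6% | At 20% (assumed) |
|---|---|---|---|
| 35 | 17.5 | 1.05 | 3.5 |
| 70 | 35 | 2.1 | 7 |
| 105 | 52.5 | 3.15 | 10.5 |
| 140 | 70 | 4.2 | 14 |

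**Would a fixed trigger settle it?** Take as an example an automatic review at 4 or more conversions in the first 18 off-pump patients, or 6 or more in the first 35, with independent conversions. Then

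P(trigger) = P(X₁₈ ≥ 4) + Σₖ₌₀..₃ P(X₁₈ = k) · P(Y₁₇ ≥ 6 − k),

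with X and Y binomial. At 6% this is 0.0201 + 0.0099 = 0.030. At assumed rates of 10, 15, 20 and 25% it is 0.169, 0.476, 0.757 and 0.914. Such a rule rarely fires falsely, but it misses a true 15% rate about 52% of the time (1 − 0.476). The cut-offs are arbitrary, so the figures support having someone look at conversions and do not support writing this particular rule into the protocol.

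**The case against.** The strongest reply is that independent oversight already exists. The protocol says the PI will consult the committee, not that the PI may, and it says so in the same sentence as the periodic review. The natural reading is that consultation is part of each review. The committee adjudicates every pump thrombosis without waiting for the PI's invitation, a masked pathologist confirms the cause of in-hospital deaths, and the IRB reviews the protocol. Both methods are described as approved, and this is a single-centre trial of 140 patients. Most of this stands. A reader might infer that the committee acts only at the PI's discretion, or that a harm signal could never reach anyone independent. The text supports neither. What the reply does not supply is a date, a by-arm table, access or authority for the committee. Adjudicating one part of one composite component is not a review of deaths, RVAD use, renal replacement, stroke, bleeding and conversions by arm.

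A second reply is that a PI who supervises every case can never be masked, because individual events and known techniques allow the by-arm picture to be rebuilt. That is right. For the same reason, labelling the arms A and B would protect little, since a row of conversions from off-pump to on-pump identifies the arm. The aim is therefore to move the comparative judgement to independent people; masking the PI is not achievable.

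A third reply is that conversion is a weak measure of this gap. The listed operative safety outcomes are 30-day mortality, chest tube output and re-exploration for bleeding, and nothing in the documents suggests conversion rates above 6%. That also stands: the conversion figures illustrate scale and do not measure the lack of independence.

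**Conclusion.** The point holds as a gap in safety oversight that should be closed. The PI reviews safety and supervises every operation. The independent committee, although consulted, has no stated schedule, by-arm data, access or authority to recommend a pause. These are facts of the text and rest on no calculation. That the PI sees comparative results is a reasonable inference and is not stated.

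Two stronger readings should not be drawn. The first is that a drifting stability test biases the treatment comparison. The test precedes the envelope, so drift changes who is enrolled, and the documents show no failure of concealment. Only decisions after randomisation could differ by arm; for conversions, the reasons and timing are recorded and the analysis is by intention to treat. The second is that the trial lacks independent oversight altogether, which the committee's existing roles and IRB review contradict.

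The effect on the trial's result cannot be sized from the documents. The conversion figures (4.2 of 70 expected at 6%, 14 at an assumed 20%) show only how large a departure could go without a required independent look.

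**What to change.** Make the existing Research Review Committee the reviewer of accumulating safety data.

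1. **Schedule.** Fix review points during enrolment, for example after 35, 70 and 105 patients reach day 30. A review at 140 would come too late to affect recruitment.
2. **Data.** The study coordinator sends de-identified by-arm tables directly to the committee: deaths, RVAD, renal replacement, stroke, re-exploration for bleeding and conversions, with the observed conversion rate set against the stated figure of under 6%.
3. **Authority.** The committee recommends continue, modify or pause to the PI and the IRB.
4. **Investigators.** They receive no comparative by-arm tabulations. The PI keeps individual event reporting.
5. **Order of work.** The committee adjudicates pump thrombosis before it opens each by-arm table.
6. **Consistency.** Amend the data-access restriction in Data and Safety Monitoring to admit the committee, and use one name for it (it is a team there and a committee in Primary Outcome Measures).
7. **Triggers.** Leave any numerical conversion threshold to the committee's charter.

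The charter should also say that these reviews carry no test for benefit. If each of three interim reviews and the final analysis used an unadjusted two-sided 0.05 test able to stop the trial, simulation of four equally spaced looks gives an overall type I error of about 12.7%. The protocol plans no such tests, and none is needed here.

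The cost is protocol wording, a short charter, about three scheduled reviews and the PI's loss of comparative interim tables. The sample size does not change, and the committee already includes a biostatistician.
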